15.1 Variables and derivations

The following vital signs parameters will be reported for this study:

- Temperature (c)
- Weight (Kgs)
- Systolic Blood Pressure (mmHg)
- Diastolic Blood Pressure (mmHg)
- Pulse (beats per minute)

15.2 Analysis

Population: Table: ITT

Listing: ITT

Statistics: Summaries of vital parameters will include descriptive statistics at each assessment for the actual and change from baseline (number of participants, mean, SD, median, minimum & maximum) (for quantitative measurements). Listing will be presented by participant, timepoint and parameter.

16. Physical and Oropharyngeal Examination

16.1 Variables and derivations

The following physical examination parameters will be reported for this study:

- Skin
- Cardiovascular
- Respiratory
- Gastrointestinal
- Neurology

16.2 Analysis

Population: Table: ITT

Listing: ITT

Statistics: The physical examination & oropharyngeal assessment will be presented in data listings and summarised as number and percentage (n and %) at all assessment timepoints. Physical & oropharyngeal examination data will be classified as normal & abnormal.

17. Primary Estimand

17.1 Incidence of adverse events (AE), serious adverse events (SAE) and adverse events of special interest (AESIs) during 12 weeks.

As per the protocol, estimand will be defined as follows:

- **Summary measure:** Number and percentage of participants experiencing an AEs, SAEs and number and percentage of participants experiencing AESIs by system organ class and by preferred term.
- **Population of interest:** COPD patients in India.
- **Key intercurrent events (ICEs):** Discontinuation of treatment (for any reason).
- **Strategy for intercurrent events:** A while on treatment strategy will be used for treatment discontinuation. This estimates the percentage of participants experiencing an AE or SAE while taking treatment. Participants that test positive for COVID-19 will immediately discontinue study treatment. Therefore COVID-19 will be included as the intercurrent event of study treatment discontinuation and will be handled with while on treatment strategy for the primary estimand.
- **Supplementary Estimand:** Incidence of adverse events (AE), serious adverse events (SAE) and adverse events of special interest (AESIs).
- A supplementary estimand will be defined using identical properties as for the primary estimand (summary measure, population of interest and key intercurrent events), however this supplementary estimand will report all AEs regardless of the discontinuation of study treatment.
- **Strategy for intercurrent events:** Treatment policy strategy will be used for treatment discontinuation. This summary will therefore be inclusive of all on-treatment and post-treatment AEs.

17.1.1 Variables and derivations

For the definition of Adverse events (AE) and Serious adverse event (SAE) refer to the protocol section 10.6.

Derivations:

- The question “Is the adverse event serious” is answered as “Yes” then respective AE will be considered as serious AEs.
- The question “Is this event an adverse event of special interest (AESI)” is answered as “Yes” then respective AE will be considered as AESI.

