8.3.4. Adverse events of special interest

Within the FF, UMEC, and VI clinical development programs for asthma/COPD, the following ICS, LAMA, and LABA class effects were considered adverse events of special interest (AESIs) ([Table 4](#)).

Table 4 Adverse Events of Special Interest (AESI) Definitions

Special interest group	Special interest subgroup	PTs/SMQs for inclusion
CV effects	Cardiac arrhythmia	Cardiac arrhythmia (SMQ), excluding congenital and neonatal arrhythmias
	Cardiac failure	Cardiac failure (SMQ)
	Cardiac ischemia	Ischemic Heart Disease (SMQ)
	Stroke	CNS haemorrhages and cerebrovascular conditions (SMQ)
	Hypertension	Hypertension (SMQ)
Pneumonia ¹	Pneumonia	Infective pneumonia (SMQ)
LRTI (excluding infective pneumonia SMQ)		Selected PTs
Decreased BMD and associated fractures		Osteoporosis/osteopenia (SMQ) Selected PTs
Hypersensitivity		Hypersensitivity (SMQ) Angioedema (SMQ) Anaphylactic reaction (SMQ)
Anticholinergic syndrome		Anticholinergic Syndrome SMQ
Gastrointestinal obstruction		Gastrointestinal obstruction SMQ
Adrenal suppression		Selected PTs
Antimuscarinic ocular effects/corticosteroid-associated eye disorders	Glaucoma (antimuscarinic/corticosteroid)	Glaucoma (SMQ)
	Cataracts (corticosteroids)	Lens disorder (SMQ)

Special interest group	Special interest subgroup	PTs/SMQs for inclusion
Effects on glucose		Hyperglycaemia/ new onset diabetes mellitus (SMQ)
Local steroid effects		Selected PTs
Urinary retention		Selected PTs
Effects on potassium		Selected PTs
Tremor		Selected PTs
Asthma/bronchospasm for asthma-related intubations and deaths		Asthma/bronchospasm SMQ
Dry mouth/drying of airway secretions		Selected PTs (narrow and broad focus) ²

Abbreviations: BMD, bone mineral density; CNS, central nervous system; CV, cardiovascular; LRTI, lower respiratory tract infection; PT, preferred term; RAP, Reporting and Analysis Plan; SMQ, standardized MedDRA queries.

1. All diagnosed pneumonias (with or without radiographic confirmation) were to be recorded on the adverse event page of the eCRF and on the pneumonia page of the eCRF. All suspected pneumonias were required to be confirmed by the presence of new infiltrates on a posteroanterior and lateral chest x-ray (≤ 48 h of suspected event) (details provided in Protocol Section 7.5.1.6).
2. Includes nasopharyngitis.

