3.2 Schedule of events

Refer to section 1.3 schedule of activities of the protocol.

4. Changes/deviations from the planned analysis

The statistical analysis/methods as described in the protocol were adopted. For secondary endpoint analysis, as mentioned in the protocol, treatment policy shall be used as supplementary estimand for secondary endpoints if >5% of the ITT participants discontinued study treatment. However as per the discussion of study team analysis will be done using treatment policy (as supplementary estimands) even if 5% do not discontinue the study treatment. That is the condition of 5% will not be applicable.

Any deviation from original statistical analysis plan will be described and justified in the SAP or final clinical study report.

5. Analysis populations

The following sets will be used for the statistical analyses:

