14.1 Variables and derivations

Adverse Events (AEs) will be coded using standard GSK dictionary, MedDRA central coding dictionary, version 26.0 or higher.

For the definition of Adverse events (AE) and Serious adverse event (SAE) refer to the protocol section 10.6.

The following parameters will be summarised for the participant's adverse events as mentioned in eCRF:

- Number of participants with at least one AEs pre treatment
- Number of participants with at least one AE during treatment
- Number of participants with at least one AE post treatment
- Number of participants with at least one Drug related AE.
- Number of participants with at least one serious AEs
- Number of participants with at least one Drug related serious AEs
- Number of participants with at least one AESI
- All Adverse Events
- Ongoing AEs
- AEs by Severity
- AEs by Outcome
- AEs by Action Taken with Study treatment
- AEs leading to Death

Derivations:

- The question "Adverse event related to study treatment" is answered "Yes," then respective AEs will be considered as treatment related AE.
- The question "Is the adverse event serious" is answered as "Yes" then respective AE will be considered as serious AEs.
- The question "Is the adverse event serious" is answered as "Yes" and the question "Adverse event related to study treatment" is answered "Yes," then respective AEs will be considered as treatment related SAEs.
- If seriousness criteria are "DEATH" and outcome of adverse event is "FATAL" then we will consider it as AE leading to death.
- Participant's primary reason for discontinuation captured in the eCRF page, study treatment discontinuation is "ADVERSE EVENT" then we will consider it as AE leading to early withdrawal from study.
- Pre- Treatment AEs: AE Start Date < Study Treatment Start Date
- Post- Treatment AE's: AE Start Date > Study Treatment Stop Date

- During Treatment AE's: Treatment Start Date \leq AE Start Date \geq Treatment Stop Date

In section 22 Appendix 2 the algorithm is given for calculation of partial date imputation for Adverse Events, and it will be used for partially missing AE, start and end date imputation.

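### The SAP counts AESIs, a component of the primary endpoint, from an eCRF yes/no answer, while the protocol defines them by MedDRA SMQs and preferred terms, and the SAP does not declare the difference

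*SAP*

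**What the plan says.** **Protocol.** Section 9.2 makes the incidence of AEs, SAEs and AESIs the primary endpoint. Section 8.3.4 contains Table 4, titled "Adverse Events of Special Interest (AESI) Definitions", whose last column gives the SMQs or preferred terms that place an event in each special-interest group. Footnote 2, attached to the row on dry mouth and drying of airway secretions, reads "Includes nasopharyngitis". No other AESI definition appears in either document.

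**SAP.** Section 17.1.1, which sets the derivations for the primary estimand, says "For the definition of Adverse events (AE) and Serious adverse event (SAE) refer to the protocol section 10.6". It gives no matching reference for AESIs, and its only AESI rule is the eCRF question: "Is this event an adverse event of special interest (AESI)” is answered as “Yes” then respective AE will be considered as AESI". Section 14.1 lists participants with at least one AESI among quantities taken from the eCRF and adds no AESI derivation to its list. The same section says "Adverse Events (AEs) will be coded using standard GSK dictionary, MedDRA central coding dictionary, version 26.0 or higher", so the coded terms will exist. Section 4, on changes from the planned analysis, says "The statistical analysis/methods as described in the protocol were adopted" and declares one departure only: the 5% discontinuation condition for the supplementary FEV1 estimand is dropped. The revision history in section 20 does not mention AESIs.

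**The concern.** The protocol makes AESI status a property of the coded term. The SAP makes it a property of an answer on a form. An event can meet one rule and not the other, in either direction.

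Nasopharyngitis is an example. Table 4 counts it under drying of airway secretions, but someone asked whether a cold is of special interest could reasonably say no. The protocol's own summary of the 52-week study in section 2.3.1 shows how broad a term-based group can be. Hypersensitivity AESIs occurred in 5% of every group, yet most of those events were judged unrelated after review.

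At stake is the participant-level AESI count in the primary estimand. This is a single-arm study, which section 4.2 justifies by the existing global data, and the AESI figures quoted in section 2.3.1 are given by AESI group, some explicitly by SMQ. A count based on the flag would not be on that basis, and a reader of the SAP would have no warning.

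**Working it through.** **1. What Table 4 contains.** Sorting its special-interest groups by the inclusion column:

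| Specified by | Groups | Number |
|---|---|---|
| SMQ only | CV effects, pneumonia, hypersensitivity, anticholinergic syndrome, gastrointestinal obstruction, ocular effects, glucose, asthma/bronchospasm | 8 |
| Selected PTs only | LRTI, adrenal suppression, local steroid effects, urinary retention, potassium, tremor, dry mouth/drying of secretions | 7 |
| Both | Decreased BMD and fractures | 1 |
| Total | | 16 |

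The preferred terms for 7 + 1 = 8 groups are not listed in either document, and the scope of the SMQs is not stated.

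**2. The two rules side by side.**

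| | Protocol Table 4 | SAP 17.1.1 |
|---|---|---|
| Deciding item | Coded preferred term | eCRF answer |
| Who or what decides | MedDRA look-up | Not stated |
| Check against the other rule | – | None stated |
| Declared as a change in SAP section 4 | – | No |

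**3. The plan's own figure.** Protocol Table 5 gives 0.8904 as the chance of at least one event among 220 participants at a risk of 1/100. Check: 1 − 0.99^220 = 0.8904, which agrees. That figure assumes every event is counted. If the flag caught a fraction Se of true AESIs, with no false flags, the chance of counting at least one would be 1 − (1 − 0.01·Se)^220: 0.863 at Se = 0.90, 0.809 at 0.75 and 0.668 at 0.50.

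**4. Effect on the reported percentage (illustration).** Let p be the true AESI incidence, Se the flag's sensitivity and f the proportion of other participants falsely flagged. All three are assumptions. N = 229 is the planned number entering treatment.

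Reported proportion = p·Se + (1 − p)·f. At p = 10% (22.9 participants):

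| Se | f | Calculation | Reported | Participants |
|---|---|---|---|---|
| 0.50 | 0 | 0.10·0.50 | 5.0% | 11.5 |
| 0.90 | 0 | 0.10·0.90 | 9.0% | 20.6 |
| 0.50 | 5% | 0.050 + 0.90·0.05 | 9.5% | 21.8 |
| 0.90 | 5% | 0.090 + 0.90·0.05 | 13.5% | 30.9 |

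The shift runs from −5.0 to +3.5 points. For scale, the 95% sampling half-width at 10% is 1.96·√(0.1·0.9/229) = 3.9 points.

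**5. Direction.** Missed and false flags cancel when f = p(1 − Se)/(1 − p). At Se = 0.75 this gives 0.05·0.25/0.95 = 1.3%, 0.10·0.25/0.90 = 2.8% and 0.15·0.25/0.85 = 4.4% for true incidences of 5%, 10% and 15%. Modest false-flag rates would therefore be enough to offset or reverse an undercount, so no direction can be claimed.

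**The case against.** The best defence is that the two texts do different jobs: Table 4 says what an AESI is, and the SAP names the field that carries the classification. Protocol 8.3.5 already expects investigators to recognise and report AESIs, so a site-level flag is natural, and SAP 17.1.1 also takes SAEs from an eCRF answer. The eCRF and its completion guidance are separate documents that were not available here and may tie the flag to Table 4. Table 4 also looks carried over: it describes what was considered an AESI in the development programmes, its first footnote cites a section 7.5.1.6 that this protocol does not have, and half its groups rest at least partly on unlisted terms. Finally, there is no hypothesis test, and all AEs are tabulated by SOC and PT, so no event is lost.

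Part of this stands. The size of any error is unknown, the example of nasopharyngitis is a possibility rather than an observation, and the SOC/PT tables would let a reader rebuild some SMQ-based groups.

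It does not remove the problem. Neither document says the flag is completed against Table 4. A site could hardly do so, because SMQ membership depends on the coded term and the selected PTs are not listed. The SAE comparison works against the defence: there the SAP points to the protocol definition, and for AESIs it does not. Tables of all AEs do not correct the participant-level AESI total. That Table 4 cannot be programmed as printed is a reason for the SAP to complete it, not to replace it without saying so.

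**Conclusion.** The concern holds. For one of three primary endpoint components, the SAP states a rule that departs from the only definition in the protocol, while section 4 says the protocol methods were adopted. This is certain from the texts and depends on no calculation.

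The effect on the reported AESI percentage cannot be determined from the documents. The range of 5.0% to 13.5% around a true 10% rests wholly on assumed values (sensitivity 50% to 90%, false flags 0 to 5%). It shows only that plausible misclassification could be of the same order as sampling error. An undercount is plausible because Table 4 is broad, but the documents do not settle the direction. AE and SAE counts are unaffected. The point should be fixed before database lock.

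**What to change.** In SAP 14.1 and 17.1.1, replace the flag rule with wording such as: *An AE is an AESI if its coded preferred term falls within an SMQ or preferred-term list of Table 4, protocol section 8.3.4.* In an appendix finalised before database lock, fix:

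- the MedDRA version, which the SAP now leaves open as 26.0 or later;
- the scope of each SMQ;
- the selected preferred terms for the 8 groups that use them.

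Keep the eCRF flag as a reconciliation check, with a listing of events where flag and coded term disagree. That listing also covers any mismatch with AESIs that sites reported under protocol 8.3.5. The SOC/PT presentation can stay; totals by special-interest group are an optional addition. If the sponsor intends the flag to be the definition, SAP section 4 must declare and justify that change.

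The cost is SAP wording and a programmed look-up on AEs that will be coded anyway; no new data are needed. The real work is settling the term lists and SMQ scope. A small drawback is that SMQs may bring in some non-specific terms, which the PT-level rows will make visible.

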17.1.2 Primary estimand analyses

Population: Table: ITT

Listing: NA

Statistics:

While on-treatment Policy: Values of the variable up to the time of the intercurrent event.

This strategy summarises the variable while the patient actually receives their randomised treatment. An example of use of this strategy is the standard approach to safety data. Adverse events in efficacy trials are usually summarised over the period while a subject is receiving the randomised treatment.

The primary estimand analysis will be performed for participants experiencing an AE, AESI & SAE while taking treatment. It will follow while on treatment policy. But if a subject discontinues treatment during this period of Visit 2-Visit 4 then values only before discontinuation point will be considered.

Treatment Policy: Actual values of the variable regardless of whether the intercurrent event has occurred.

This approach requires collection of data after the intercurrent event of interest (e.g. continued collection if a patient discontinues treatment) and corresponds to a full ITT approach. If the patient also withdraws from the study, then this becomes a missing data problem. The supplementary estimand analysis will be performed for participants experiencing AE, AESI & SAE while taking treatment and post treatment. It will follow treatment policy.

Summary will be presented as the number of participants experiencing AE, AESI & SAE including the incidence of AEs by alphabetically preferred term (PT) sorted by decreasing frequency within the system organ class (SOC). Number and proportion of participants with AEs will be presented. Both number of participants, number of event (One participant may be counted more than once) and percentage will be provided.

Note: If there are uncoded adverse events, then the uncoded category will be added in the AEs by SOC/PT summary tables.

For the supplementary analysis refer to the SAP section 14.

18. Secondary efficacy estimands

18.1 Change from baseline in trough FEV1 on Day 85 and Day 28

As per the protocol, estimand will be defined as follows:

- **Summary measure:** Mean change from baseline in trough FEV1 on Day 85.
Mean change from baseline in trough FEV1 on Day 28.
- **Population of interest:** COPD patients in India.
- **Key intercurrent events (ICEs):** Discontinuation of treatment.
- **Strategy for intercurrent events:** A hypothetical strategy will be used for treatment discontinuation. This estimates the effect under the hypothetical scenario that participants had not discontinued treatment. Participants that test positive for COVID-19 will immediately discontinue study treatment. Therefore COVID-19 will be included as the intercurrent event of study treatment discontinuation and will be handled with hypothetical strategy for the secondary estimands.
- **Supplementary Estimands:**
Mean change from baseline in trough FEV1 on Day 85.
Mean change from baseline in trough FEV1 on Day 28.
A supplementary estimand will be defined using identical properties (summary measure, population of interest and key intercurrent events), however this supplementary estimand will report the actual values recorded regardless of the discontinuation of study treatment.
- **Strategy For ICE under Supplementary Estimands:** A supplementary estimand will be estimated using treatment policy strategy for the intercurrent event of treatment discontinuation unrelated to the COVID-19 pandemic and using hypothetical strategy for the intercurrent event of treatment discontinuation related to the COVID-19 pandemic.
- **Treatment Policy:** Actual values of the variable regardless of whether the intercurrent event has occurred. This approach requires collection of data after the intercurrent event of interest (e.g. continued collection if a patient discontinues treatment) and corresponds to a full ITT approach. If the patient also withdraws from the study, then this becomes a missing data problem.

18.1.1 Variables and derivations

- Trough FEV1 on Day 85 is defined as the mean of the FEV1 values obtained 24 hours after morning dosing on Day 84.
- Trough FEV1 on Day 28 is defined as the mean of the FEV1 values obtained prior to dosing on Day 28

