8.1. Efficacy Assessments

8.1.1. Spirometry

Spirometry measurements will be obtained using spirometry equipment that meets or exceeds the minimal performance recommendations of the American Thoracic Society (ATS) [[Miller](#), 2005]. All sites will use standardised spirometry equipment provided by an external vendor. All participants will have spirometry performed at - each scheduled clinic visit during the treatment period. For FEV₁ and FVC determinations, at least 3 acceptable spirometry efforts (with no more than 8) should be obtained. Acceptable spirometry efforts should have a satisfactory start of test and end of test (e.g. a plateau in the volume-time curve) and be free from artifacts due to cough, early termination, poor effort, obstructed mouthpiece, equipment malfunction, or other reasons [[Miller](#), 2005].

The largest FEV₁ and FVC from the 3 acceptable efforts should be recorded, even if they do not come from the same effort.

Spirometry must be performed as follows:

- Started approximately between 6:00AM and 11:00AM.
- After completing the CAT health outcomes assessment (Visit 1 only)
- After withholding albuterol/salbutamol for ≥ 4 hours.
- Before the morning dose of maintenance COPD medication or study treatment.
- Participants should refrain from smoking and/or vaping and use of a water pipe for 1 hour prior to each pulmonary function test.
- Participants should abstain from drinking beverages with high levels of caffeine such as tea and coffee for 2 hours prior to each pulmonary function test.
- Participants should not consume intoxicant for 8 hours prior to each pulmonary function test
- Vigorous exercise should be avoided for at least 1 hour prior to each pulmonary function test.

A full description of the timing and conduct of spirometry procedures is provided in the SRM.

Spirometry equipment will be provided through a centralized vendor.

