9.3.1. Efficacy Analysis

All efficacy analyses will be performed on the ITT Population.

The efficacy endpoints are change from baseline in trough FEV1 on Day 85, and Day 28.

The estimands for these endpoints are defined below:

- Endpoint:
 - change from baseline in trough FEV1 on Day 85 (trough FEV1 on Day 85 is defined as the mean of the FEV1 values obtained 24 hours after morning dosing on Day 84)
 - change from baseline in trough FEV1 on Day 28 (trough FEV1 on Day 28 is defined as the mean of the FEV1 values obtained prior to dosing on Day 28)
- Summary measure:
 - mean change from baseline in trough FEV1 on Day 85
 - mean change from baseline in trough FEV1 on Day 28
- Population of interest: COPD patients in India.
- Key intercurrent events: discontinuation of treatment
- Strategy for intercurrent events: a hypothetical strategy will be used for intercurrent event of treatment discontinuation. Trough FEV1 data collected up to the time of

treatment discontinuation will be used in the analysis. This estimates effect under the hypothetical scenario that participants do not discontinue treatment.

- Participants that test positive for COVID-19 will immediately discontinue study treatment. Therefore COVID-19 will be included as the intercurrent event of study treatment discontinuation and will be handled with hypothetical strategy for the estimand.

The endpoint of change from baseline in trough FEV1 will be analysed using a mixed model repeated measures (MMRM) analysis. The analysis will include change from baseline in trough FEV1 at Day 28, and Day 85. Mean change from baseline in trough FEV1 will be summarised and presented with 95% confidence interval by visit. Trough FEV1 collected after treatment discontinuation will be set to missing. Missing data will be assumed to be missing at random (MAR).

Taking prohibited medication during the treatment period is an important protocol deviation (PD) and will be included in the PD summary. However, this is not considered as an intercurrent event for the estimands.

A supplementary estimand will be estimated using treatment policy strategy for the intercurrent event of treatment discontinuation unrelated to the COVID-19 pandemic and using hypothetical strategy for the intercurrent event of treatment discontinuation related to the COVID-19 pandemic. This supplementary treatment effect will only be estimated if >5% of the ITT subjects discontinued study treatment.

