6.1 Baseline

Baseline is defined as the last non-missing observation made prior to the first administration of study treatment including those from unscheduled visits. If time is not collected, Day 1 assessments are assumed to be taken prior to first dose and used as baseline. Unless otherwise stated, if baseline data is missing no derivation will be performed and baseline will be set to missing.

Participants who prematurely withdrew from study will not be replaced. For ECG, if the latest, non-missing pre-dose values is from triplicate, the subject level baseline is defined as the mean of triplicate baseline assessments.

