18.1.2 Secondary estimand analyses

Population: Table: ITT
Listing: ITT

Statistics: The mean change in FEV1 values from baseline to Day 28 and Day 85 will be summarized using descriptive statistics (mean, median, SD, minimum, maximum, and number with missing values).

Only scheduled spirometry observations will be used for the analysis and unscheduled spirometry observations will be presented in data listing.

The MMRM model will be used for analysis of the change in FEV1 values from baseline to Day 28 and Day 85. Least-square means, standard error, 95% CI derived from the analysis model will be displayed by day for two models within the MMRM output. The first model will include change from baseline in FEV1 values as response variable, FEV1 values at baseline and day as covariates and an interaction between FEV1 values at baseline and day. Day will be specified as the repeated effect, and with SUBJECT option to account for the repeated measures within subjects. OM will be used in lsmeans statement. An unstructured covariance structure will be used to model the within-participant variability. If this analysis fails to converge, the following covariance structures will be tested in order:

1. Toeplitz with heterogeneity
2. Autoregressive with heterogeneity, by day
3. Compound symmetry with heterogeneous variances, by day
4. Toeplitz
5. Autoregressive
6. Compound symmetry without heterogeneous variances, by day

The first covariance structure that converges will be used. The Kenward-Roger approximation will be used to estimate denominator degrees of freedom. Significance tests will be based on least-squares mean using Type III sum of squares.

The second model will use absolute FEV1 values as response variable, whilst all other components remain the same as described above.

Through FEV1 data collected up to the time of treatment discontinuation will be used in the analysis. This estimates effect under the hypothetical scenario that participants do not discontinue treatment. Through FEV1 collected after treatment discontinuation will be set to missing. Missing data will be assumed to be missing at random (MAR).

A supplementary estimand will be estimated using treatment policy strategy for the intercurrent event of treatment discontinuation unrelated to the COVID-19 pandemic and using hypothetical strategy for the intercurrent event of treatment discontinuation related to the COVID-19 pandemic.

19. Other assessments

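### Does calling trough FEV1 a mean, when the largest effort is what gets recorded, make change from baseline compare unlike quantities?

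*SAP*

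**What the plan says.** The endpoint definitions use a mean. For Day 85, SAP 18.1.1 has "Trough FEV1 on Day 85 is defined as the mean of the FEV1 values obtained 24 hours after morning dosing on Day 84", and for Day 28 "Trough FEV1 on Day 28 is defined as the mean of the FEV1 values obtained prior to dosing on Day 28". SAP section 2 and protocol sections 1.1, 3 and 9.3.1 carry the same definitions. None of these places says how many values are averaged, or whether they are efforts or time points.

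The measurement rule is in protocol 8.1.1. At a session, "at least 3 acceptable spirometry efforts (with no more than 8) should be obtained", and then "The largest FEV₁ and FVC from the 3 acceptable efforts should be recorded". The rule covers all clinic visits scheduled in the treatment phase. The Schedule of Activities (protocol 1.3) has a single row for baseline and trough spirometry, marked at Visits 2, 3 and 5, with no repeat time points. Its footnote d calls the Visit 2 measurement a trough FEV1 and sets the same pre-dose conditions for Visits 2 and 3.

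The general baseline rule is in SAP 6.1: "Baseline is defined as the last non-missing observation made prior to the first administration of study treatment including those from unscheduled visits". The only averaging it mentions is for triplicate ECGs. SAP 18.1.2 says of spirometry: "Only scheduled spirometry observations will be used for the analysis".

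**The concern.** Three statements about one number do not use the same words: a mean in the endpoint, a maximum in the measurement section, and a latest value in the baseline rule. The largest of several efforts can never be below their mean. If baseline were the session's largest effort and follow-up the session's average, the change would be understated even with no true change at all.

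This is a single-arm study, so no control group would cancel such an offset. Change in trough FEV1 is the only efficacy endpoint, and the confidence interval would not reveal a shift of this kind. Separately, SAP 6.1 admits unscheduled values as baseline while SAP 18.1.2 keeps unscheduled spirometry out of the analysis, so two programmers might choose different baselines for the same participant.

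**Working it through.** **The plan's own figure.** Protocol 9.2 states a precision of 32 mL (half width of the 95% CI) for 220 evaluable participants and a residual SD of 240 mL.

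- Normal: 1.96 × 240 / √220 = 470.4 / 14.83 = 31.7 mL.
- t with 219 df: 31.9 mL.

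Both round to 32 mL. The wording question does not affect this figure.

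**Size of an offset under each possible derivation.** Assume three independent normal efforts per session with common within-session SD s and no true change. The documents do not give s. The expected maximum of three standard normals is 3 / (2√π) = 0.846 and the expected mean is 0, so the largest effort exceeds the session mean by 0.846 × s on average. The last column is a simulation of 400,000 participants with s = 50 mL.

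| Baseline | Follow-up | Expected offset | Simulated, s = 50 mL |
|---|---|---|---|
| Largest | Largest | 0 | 0.02 mL |
| Mean | Mean | 0 | -0.04 mL |
| Last effort | Mean | 0 | -0.13 mL |
| Largest | Mean | -0.846 × s | -42.35 mL |

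Only the last row produces a bias. Its size over an assumed range of s:

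- s = 10 mL: -0.846 × 10 = -8 mL
- s = 30 mL: -0.846 × 30 = -25 mL
- s = 50 mL: -0.846 × 50 = -42 mL
- s = 100 mL: -0.846 × 100 = -85 mL

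It would equal the stated 32 mL precision at s = 32 / 0.846 = 38 mL.

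**Which row the documents describe.**

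1. Protocol 8.1.1 gives one recording rule, the largest value, without separating Visit 2 from Visits 3 and 5.
2. The Schedule of Activities provides one spirometry session at each of those visits, so there is no second time point to average.
3. Each visit therefore supplies one recorded FEV1. The mean of one value is that value, and the latest pre-dose value is the Visit 2 value recorded under the same rule.

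That is the first row, with an offset of 0 mL. The last row needs 8.1.1 obeyed at Visit 2 and set aside at Visits 3 and 5, which neither document says.

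**Unscheduled values.** SAP 6.1 is a general rule for all variables. SAP 18.1.2 is specific to spirometry, and the revision history shows its treatment of unscheduled spirometry was clarified in version 3.0 (29-Feb-2024), after the initial version of 06-Jun-2023. A later, specific rule ordinarily governs a general one. There is also little room for conflict: no spirometry is scheduled before Visit 2, and footnote k has the first dose given in clinic at that visit. The two rules diverge only if the Visit 2 session is missing or an extra reading is taken after it and before dosing.

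**The case for a change.** The best argument for a change is that the definition is repeated in several places and should mean something. The reading that is plainly like for like leaves the word mean with no work to do. If the vendor's system exports every effort, a programmer could average the follow-up efforts because the endpoint says so, yet take the largest at baseline because SAP 6.1 has no averaging rule for FEV1. Baseline FEV1 is also a covariate, with a day interaction, in the MMRM. The edit would be cheap, and the rule is best settled before data lock.

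Part of this stands. The word is loose, SAP 6.1 has no FEV1-specific line, and a cross-reference to 18.1.2 would be tidier. But the harmful derivation requires a programmer to treat the same measurement differently at different visits, against 8.1.1 and against a schedule that puts baseline and trough in one row. If all efforts were stored, averaging at every visit would be just as unbiased as taking the largest at every visit, and averaging follow-up against the last baseline effort would be noisier but also unbiased in expectation. Protocol 8.1.1 further leaves the full spirometry procedure to the Study Reference Manual, which is not among the documents, so the absence of a single rule there cannot be assumed. The argument shows that a misreading is possible, not that the plan leads to one.

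**Conclusion.** No change follows. With protocol 8.1.1 applied at every visit, baseline and follow-up are the same kind of value and the offset is 0 mL. The alternative, about -8 to -85 mL for an assumed within-session SD of 10 to 100 mL, depends on a mixed derivation that neither document describes and on an SD that neither document gives. The unscheduled-value question is settled by reading the specific spirometry rule over the general baseline rule, and it could touch only a participant with a missing Visit 2 session or an extra pre-dose reading.

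The conclusion assumes that sites record one FEV1 per session as 8.1.1 directs, or, if efforts are stored separately, that the analyst summarises them in the same way at Visits 2, 3 and 5. The endpoint is secondary and no hypothesis is tested, so no error rate depends on it. This is a drafting looseness that a competent analyst resolves in the ordinary course of programming, with no demonstrated gain from revising the plan.
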